Despite these encouraging findings on the beneficial effects of resistance-based exercise on sarcopenia and CAD separately, no study has been done to examine its effects on patients having the co-existence of sarcopenia and CAD, leaving a significant gap in the literature. Indeed, enabling this vulnerable cohort to adopt and maintain regular resistance exercise remains a great challenge. Older adults have reported perceived difficulty, time constraints and boredom as obstacles to resistance exercise.¹⁸ An effective yet sustainable intervention needs to address these challenges/obstacles. Previous studies have highlighted the importance of enhancing older people's self-efficacy in performing exercise in order to improve exercise adoption and adherence.^{19,20} Moreover, opportunities to resistance training, indeed, emerge around the clock in the routine of an individual. Assisting older adults to integrate exercise into daily activities can maximize the training benefits and overcome barriers to exercise, and thus improve exercise adoption and adherence.²¹ Therefore, this study aims to develop a strength-building lifestyle-integrated intervention for sarcopenic CAD patients and to examine the feasibility and preliminary effects of this intervention on skeletal muscle mass, muscle strength, physical performance, cardiac-related functional status and health-related quality of life (HRQoL), psychological distress, major adverse cardiovascular and cerebral events (MACCE) and hospital readmission rates. Physical performance will be the primary outcome, while the remaining will be the secondary outcomes.

Research plan and methodology

Study design

This study will include an assessor-blinded two-arm prospective pilot randomized controlled trial (RCT) and a qualitative study to determine the feasibility, acceptance and engagement experience of the participants in the strength-building lifestyle-integrated intervention with assessments measured at baseline, 3 months and 6 months after randomization.

Study setting and participants

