This study will recruit subjects in Care for Your Heart, a cardiac patient mutual support organization. Patients fulfilling the following eligibility criteria will be invited to join the study: 1) Chinese adults with a confirmed diagnosis of CAD; 2) age ≥ 60 years or older; 3) presence of sarcopenia according to the diagnostic criteria defined by the Asian Working Group for Sarcopenia²²: low skeletal muscle mass (measuring the appendicular skeletal muscle mass with bioelectrical impedance analysis: <7.0 kg/m² for men and <5.7 kg/m² for women), accompanied by low muscle strength (handgrip strength <28 kg for men and <18 kg for women); 4) free from ischemic symptoms when performing activities of daily living; 5) living in the community. Patients who cannot read Chinese or with impaired cognition (Abbreviated Mental Test score ≤ 6) or communication, a pacemaker or implantable cardioverter defibrillator precluding the use of bioelectrical impedance analysis for body composition assessment, physical limitations precluding exercise training, with any contraindication for exercise, any terminal or unstable conditions (e.g., malignant arrhythmia, severe aortic stenosis, cancer), admitted or recently completed a structured cardiac rehabilitation program within the past 6 months will be excluded.

The sample size for this pilot study was estimated based on the primary outcome (i.e., functional capacity) to be measured by the Short Physical Performance Battery (SPPB). The literature indicated the minimal clinically importance difference is >1 point of SPPB²³ and the SD estimate is 4.2 in the population with cardiovascular disease, giving rise to the standardized effect size as 0.28. According to the method proposed by Whitehead et al.,²⁴ a sample size of 20 per study arm for the pilot study would give the future main trial 80% power at 5% level of significance to detect the between-group changes in the primary outcome at post-intervention time points. The total sample size is therefore 40. They will be randomly allocated in a 1:1 ratio, to receive the strength-building intervention or usual care. All participants in the intervention group will be invited to take part in a face-to-face qualitative interview to explore the feasibility and acceptability of the intervention. The interviews will be conducted individually in the center of the Care For Your Heart. Each interview will be audio-recorded and will last for approximately 60 minutes.

Control group: Usual care

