Care For Your Heart, and posters in the center. A research assistant will screen the eligibility of the potential participants at the center of Care for Your Heart by measuring the calf circumference to identify patients with possible sarcopenia. A non-elastic measuring tape will be used to measure both calves, those individuals with the maximum value meeting the guideline-specified cut-offs (<34 cm in male; <33 cm in female) will be invited to undergo a more in-depth evaluation according to the eligibility criteria of this study. All eligible patients will be invited to participate. After obtaining the written informed consent, the research assistant will collect the baseline data (T0), then he/she will randomly assign participants into the intervention or control group with block randomization to ensure even distribution of participants in the two study groups over the study period. Patients will be allocated chronologically in a 1:1 ratio by using a computer-generated random sequence to determine the block size (4, 6 and 8) and respective study group allocation. The group allocation will be determined according to the random sequence codes placed in sealed opaque envelopes. Participants in the intervention group will receive the strength-building intervention whereas the control group will receive usual care. To minimize biases, another independent research assistant who is blinded to the group allocation will be responsible for collecting post-intervention data at another two time points (T1 and T2) in the center of the Care For Your Heart. Each assessment will last for approximately 30 minutes.

Data analysis

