Statistical analysis of the outcome comparisons will be performed on the basis of the intention-to-treat principle. Descriptive statistics will be used to describe the characteristics of the sample, the feasibility of, acceptance, and compliance with the intervention. The baseline characteristics will be compared between the study groups using a t-test, chi-square test or Fisher's exact test where appropriate. Repeated measure ANOVA will be used to determine the effects of the intervention by comparing differential between group changes across the 3 time-points. All statistical analyses will performed using IBM SPSS 27.0. All statistical tests will be two-sided, and a p-value of less than 0.05 will be considered statistical significant. Content analysis will be used to analyze the qualitative data. These data will be used to optimize the intervention design and feasibility for the full scale randomized controlled trial.

References:

2. World Health Organization. Cardiovascular diseases. 2021; [https://www.who.int/news-room/fact-sheets/detail/cardiovascular-diseases-\(cvds\)](https://www.who.int/news-room/fact-sheets/detail/cardiovascular-diseases-(cvds)), 2021.

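### Intention-to-treat is paired with repeated-measures ANOVA and no missing-data rule, so in its standard form the analysis becomes one of completers once a T1 or T2 visit is missed; the loss is modest and the fix cheap

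*Combined protocol and SAP*

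**What the plan says.** The Data analysis section opens with the principle: "Statistical analysis of the outcome comparisons will be performed on the basis of the intention-to-treat principle". The only method it names for intervention effects is this: "Repeated measure ANOVA will be used to determine the effects of the intervention by comparing differential between group changes across the 3 time-points". The t-test, chi-square test and Fisher's exact test in the same paragraph are for baseline characteristics. On software it says "All statistical analyses will performed using IBM SPSS 27.0", without naming the procedure.

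Three other places bear on the point:

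- **Data collection procedure and randomization.** T0 comes before allocation: "the research assistant will collect the baseline data (T0), then he/she will randomly assign participants into the intervention or control group". A blinded assistant is then responsible for "collecting post-intervention data at another two time points (T1 and T2) in the center of the Care For Your Heart". No substitute for a missed visit is described.
- **Study setting and participants.** "The total sample size is therefore 40", that is 20 per arm, with no allowance for attrition. On variability of the Short Physical Performance Battery (SPPB), "the SD estimate is 4.2 in the population with cardiovascular disease".
- **Background, study aim.** The purpose is "to examine the feasibility and preliminary effects of this intervention on skeletal muscle mass" and on the other listed outcomes, with physical performance primary.

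No section defines an analysis set, an imputation method, a rule for missed visits or a sensitivity analysis.

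**The concern.** Classical repeated-measures ANOVA needs a value at each of T0, T1 and T2. Someone who attends T1 but misses T2 is removed altogether, and the T1 value already collected is not used. The principle (everyone as randomised) and the standard form of the method (everyone with complete data) then describe different populations.

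Both follow-ups require attendance at the centre, the later one 6 months after randomisation, in people aged 60 or over with coronary disease and sarcopenia, so some missed visits are plausible.

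Two things are at stake. One is precision, because SPPB values that were paid for are discarded. The other is possible bias, in either direction, if loss is related to outcome and works differently in the two arms. What suffers is a preliminary effect estimate that will inform a full-scale trial, not a definitive test.

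**Working it through.** **Inputs.** From the documents: 20 per arm (2 × 20 = 40), three time-points, SPPB SD 4.2. Assumed: missing rates (the plan gives none, so there is no attrition figure to reproduce), equal correlation ρ between any two visits with range 0.5 to 0.8, and the same missing rate in both arms.

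**1. Who is dropped.** If each follow-up visit is missed independently with probability m:

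- complete at all visits: 40 × (1 − m)²
- dropped although one follow-up value exists: 40 × 2m(1 − m)

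| m | Attend T1 | Complete | Dropped with one follow-up value |
|---|---|---|---|
| 5% | 38 | 36.1 | 3.8 |
| 10% | 36 | 32.4 | 7.2 |

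At m = 5% the chance that at least one of 40 is incomplete is 1 − (0.95²)⁴⁰ = 0.98. Under even light loss the question will almost certainly arise.

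**2. Precision.** The comparison uses one model on two data sets: T0, T1 and T2 as responses, a common T0 mean, and treatment effects at T1 and T2. It is fitted to all observed values and then to completers only. The percentages therefore isolate the handling of missing visits and include no gain from using baseline better.

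For completers with n per arm, SE = SD × √[(1 − ρ²) × 2/n]. At m = 10%, n = 20 × 0.81 = 16.2:

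- ρ = 0.5: 4.2 × √(0.75 × 2/16.2) = 1.278; all observed data give 1.206, which is 5.6% smaller.
- ρ = 0.8: 4.2 × √(0.36 × 2/16.2) = 0.885; all observed data give 0.832, which is 6.0% smaller.

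The absolute gain in SE is about 0.07 and 0.05 points. The all-data SEs come from inverting the expected information matrix summed over the missing-data patterns. The SD cancels from the percentages, so they do not depend on 4.2 being right.

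| Pattern (assumed) | Reduction in SE at T1 | Reduction in SE at T2 |
|---|---|---|
| Independent, 5% per visit | 2.8–3.0% | 2.8–3.0% |
| Independent, 10% per visit | 5.6–6.0% | 5.6–6.0% |
| Loss only after T1, 10% | 5.1% | 0.6–1.0% |
| Loss only after T1, 20% | 10.6% | 1.1–2.0% |
| Loss only after T1, 30% | 16.3% | 1.7–3.0% |
| Both visits missed, 10–30% | 0% | 0% |

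For loss only after T1, the T1 figure is 1 − √(1 − m): for example, 1 − √0.9 = 0.051.

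**3. Bias, direction only.** Large-sample simulations used an assumed true difference of 1.0 point, SD 4.2, and loss at T2 depending on the T1 value. The quantity is the completers' difference in change from T0 to T1.

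- 20% loss per arm for the same reason (low T1): about 1.0.
- 30% loss in the intervention arm and 10% in control, both from low T1: about 1.34 at ρ = 0.5 and 1.20 at ρ = 0.7.
- About 21% loss in each arm, from low T1 in the intervention arm and high T1 in control: about 1.76 at ρ = 0.5 and 1.44 at ρ = 0.7.

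The difference in change to T2 stayed near 1.0 throughout, because with equal correlations selection on T1 moves T0 and T2 alike. The third case shows that equal rates are not enough: the reasons must also match. These are constructed examples and say nothing about how large bias would be in this trial.

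**The case against.** The best case against is that this is an omission, not a contradiction. The plan never says incomplete cases will be excluded and does not name the SPSS procedure, so exclusion follows from the method's standard form and not from a stated rule. That stands, and it limits the claim. A reader might infer that the plan breaches intention-to-treat as written. The documents do not support that: with complete follow-up there is no conflict. But keeping partial records in SPSS means a mixed model (or imputation first), and the plan names neither. Silence leaves the choice open until the data have been seen.

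The effect is also small. At 5% or 10% missing the gain is about 3% or 6%; at T2 it is at most 3% when loss follows T1; and it is nil for people who miss both visits, a common form of dropout. The 16% figure needs 30% loss, all of it after T1. This stands too. The assessments take about 30 minutes at the centre from which participants are recruited, so heavy attrition is not evident from the text.

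Two further inferences should be resisted. One is that the pilot's effect estimate will be biased: that requires loss related to outcome that differs by arm, and the documents give no information on either. The other is that similar dropout rates would settle the matter, which the third simulated case contradicts.

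Finally, one sentence on incomplete cases might seem enough. But a sentence cannot make the classical method use a partial record, so some change of method or an imputation step is needed anyway.

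**Conclusion.** The concern holds in limited form and should be fixed. The plan states intention-to-treat, names repeated-measures ANOVA as its only effect analysis and gives no missing-data rule; in its standard form that analysis is of completers as soon as a T1 or T2 visit is missed.

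The precision figures above rest on assumed missing rates and visit correlations of 0.5 to 0.8. Bias is about nil only if loss is random, or has the same rate and the same reasons in both arms; otherwise it can go either way, and no size is claimed. The benefit of changing the plan is a modest improvement in a pilot's preliminary effect estimate, plus an analysis population that matches the stated principle. The gap in the text is certain. How much it costs depends on attrition that cannot be known from the documents.

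**What to change.** In the Data analysis section, replace repeated-measures ANOVA for SPPB and for every other continuous outcome it serves: muscle mass, handgrip strength, the Seattle Angina Questionnaire, MacNew and PHQ-4. Changing SPPB alone would leave the others without a named analysis.

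- **Model.** A linear mixed model for repeated measures (SPSS MIXED), by assigned arm. T0, T1 and T2 are all responses, with one common T0 mean (justified because T0 precedes randomisation), visit terms, treatment-by-visit terms at T1 and T2, and unstructured covariance. Every randomised participant with a T0 value is included.
- **Reporting.** Treatment contrasts at T1 and T2 with 95% confidence intervals, the missing-at-random assumption stated, and missing visits by arm, which is also useful feasibility information.
- **Optional, SPPB only.** Multiply impute missing T1 and T2 values from arm, T0 and any observed follow-up value. Then shift the imputed values in both directions, for example −2 to +2 points, in each arm in turn; 1 point is the plan's own benchmark for an important difference. Expected movement is small: shift × (missing ÷ 20), so 2 of 20 missing with a 2-point shift moves the contrast by 0.2, and 4 of 20 by 0.4.

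The cost is a rewritten paragraph and, if wanted, one extra analysis. No participants, visits or software are added. The downside is that the model relies on missing-at-random, does not repair loss driven by unobserved outcomes, and adds little for people with no follow-up.

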Various methods will be used to monitor and optimize the fidelity of the study intervention. Assessments and record forms will be use to document the exercise prescription and progression. Participants’ attendance, exercise dose, performance and training response will be documented. A standardized manual will be developed to guide the delivery of each education session. The manual will also delineate the principles of exercise prescription and progression. Moreover, the 30% of the intervention sessions will be randomly selected

for fidelity monitoring by the principal investigator. Face-to-face sessions, in-person and remotely supervised sessions will be videotaped with participants' consent. Two post-doctoral fellows, who will be independent of the team will review the recorded videos and complete a performance checklist. The collected data will be used to evaluate the feasibility of the intervention.

Outcome evaluation

The following measuring tools/methods will be used for outcome evaluation at baseline (T0), immediate post-intervention (T1), and 3 months post-intervention (T2). Physical performance will be the primary outcome, while the rest will be the secondary outcomes.

Physical performance: The Short Physical Performance Battery³¹ will be used to assess physical performance and is well validated and widely adopted in clinical and research settings. It is a brief performance-based assessment consisting of 3 timed-tasks, including standing balance, walking speed, and chair stand tests. The timed results will be rescaled to obtain a score ranging from 0 to 12, higher scores indicate better physical performance.

Muscle mass and strength: The appendicular skeletal muscle mass (ASM) will be measured with the bioelectrical impedance analysis (In-Body). This is one of the gold-standard evaluation tools suggested by international guidelines for assessment of muscle mass. It is widely used in research and hospital setting for clients with sarcopenia. The muscle strength will be measured with a hydraulic dynamometer (Jamar). The standard protocol suggested by international guidelines will be followed, the maximum reading of at least 2 trials using the dominant hand in a maximum-effort isometric contraction will be recorded.

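### Baseline SPPB is analysed as a response, and no single between-group effect with a confidence interval is prespecified; a baseline-adjusted T1/T2 model would usually be more precise

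*Combined protocol and SAP*

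**What the plan says.** In the combined protocol and SAP, Outcome evaluation names physical performance, measured by the SPPB (0 to 12), as the primary outcome. It is assessed at T0 (baseline), T1 (end of intervention) and T2 (three months later). Data collection procedure and randomization puts baseline measurement before allocation: "the research assistant will collect the baseline data (T0), then he/she will randomly assign participants".

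The comparative analysis is given in Data analysis: "Repeated measure ANOVA will be used to determine the effects of the intervention", by "comparing differential between group changes across the 3 time-points". Tests are two-sided at 5%. The section names no covariate, primary time point, contrast, effect estimate or confidence interval. It also plans significance tests at baseline: "The baseline characteristics will be compared between the study groups using a t-test, chi-square test".

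The sample-size paragraph, under Study setting and participants, says the future main trial is to have power "to detect the between-group changes in the primary outcome at post-intervention time points". The time points are plural and none is singled out.

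**The concern.** Since T0 precedes randomisation, the intervention cannot affect it. Entered as a third response, it carries no treatment effect. Its value lies in explaining variation in the later scores, and covariate adjustment uses that information best. Comparing changes does subtract baseline, but with a fixed slope of 1 and not the slope the data support.

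The group-by-time test over three occasions asks whether the two mean profiles are parallel. It does not say by how much the groups differ, or when. If the group main effect were read instead, it would include T0: a true 1-point effect at both T1 and T2 would average (0 + 1 + 1)/3 = 0.67.

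This is a pilot for preliminary effects, sized with a main trial in mind. To plan that trial, the sponsor needs an SPPB difference with its CI, a residual SD and the baseline-to-follow-up correlation. The plan commits to none of these. With no contrast named, T1, T2 or an average could be emphasised after the results are known.

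The baseline significance tests add nothing: under random allocation their null hypothesis is known to be true.

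**Working it through.** **Inputs from the documents (sample-size paragraph):** SD 4.2; n = 20 per arm; a 1-point SPPB difference as the reference effect; two-sided 5%. The paragraph's standardised effect of 0.28 does not follow from these inputs (1/4.2 = 0.238). That is a separate matter and is not used here.

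**Assumed, not in the documents:** within-person correlation rho, equal between all pairs of visits (compound symmetry); normal scores; no dropout.

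**Step 1: variance of the group contrast.** Write the variance as k × 2 × SD²/n. The factor 1 + 1/36 is the finite-sample cost of estimating the baseline slope with 40 participants.

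- T1, change from baseline: k = 2(1 − rho)
- T1, adjusted: k = (1 − rho²)(1 + 1/36)
- T1/T2 average, change: k = 1 + (1 + rho)/2 − 2 rho
- T1/T2 average, adjusted: k = [(1 + rho)/2 − rho²](1 + 1/36)

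At rho = 0.7 the average gives 1 + 0.85 − 1.40 = 0.45 for change and (0.85 − 0.49) × 1.0278 = 0.370 adjusted. The ratio is 0.822.

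| rho | T1 ratio (adjusted/change) | Average ratio | Variance cut, T1 | Variance cut, average |
|---|---|---|---|---|
| 0.5 | 0.771 | 0.685 | 23% | 31% |
| 0.7 | 0.874 | 0.822 | 13% | 18% |
| 0.8 | 0.925 | 0.891 | 8% | 11% |

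At T1 the ratio is 0.976 at rho 0.9 and 1.002 at rho 0.95, so the gain has gone by then.

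**Step 2: 95% CI half-width for the T1/T2 average.** Half-width = t × 4.2 × √(k × 2/20), with t = 2.024 on 38 df (change) or 2.026 on 37 df (adjusted). At rho 0.7 this is 2.024 × 4.2 × √0.045 = 1.80 against 2.026 × 4.2 × √0.037 = 1.64.

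| rho | Change | Adjusted |
|---|---|---|
| 0.5 | 2.33 | 1.93 |
| 0.7 | 1.80 | 1.64 |
| 0.8 | 1.47 | 1.39 |

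**Step 3: power at rho 0.7**, from non-central F (2 and 76 df, no sphericity correction) and non-central t.

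| Effect at T1, T2 (points) | Planned 2-df test | Adjusted average | Adjusted T1 only |
|---|---|---|---|
| 1, 1 | 15% | 23% | 17% |
| 2, 2 | 49% | 67% | 53% |
| 2, 1 | 38% | 44% | 53% |
| 1, 2 | 38% | 44% | 17% |
| 2, 0 | 49% | 23% | 53% |

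The ranking is not uniform. The average loses clearly when the effect exists at one time point only, and T1 alone loses when the effect builds after T1. With AR(1) correlation 0.8 and effects 2 then 1, simulation gave 42% for the adjusted average against 44% for the planned test.

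**Step 4: where the power gain comes from.** For a sustained 1-point effect at rho 0.7, the 2-df test has 15.2%, a 1-df change contrast on the T1/T2 average 19.4%, and the adjusted average 22.6%. Naming a contrast adds 4.2 percentage points and baseline adjustment a further 3.2.

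**Step 5: validity.** In simulation (20,000 trials per scenario) type I error was about 5% for both approaches under compound symmetry. Under AR(1) the uncorrected 2-df test ran at 5.1% to 5.7%.

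**The case against.** The strongest reply is that nothing in the plan is wrong: the test is valid, it already compares changes, and swapping one valid analysis for a usually more efficient one is a preference. Validity is granted. But the adjustment uses a measurement already collected and costs one degree of freedom, and the missing contrast and interval are a gap whatever the correlation.

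A second point stands in part. At rho 0.7 more than half of the power gain for a sustained 1-point effect comes from moving to one degree of freedom (Step 4), and a contrast within the planned ANOVA could supply that. The variance and half-width comparisons do not have this problem: both sides are 1-df contrasts, so they isolate the adjustment.

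Third, rho and the shape of the effect over time are unknown. Supervision tails off over the 12 weeks, so a sustained effect is not assured. This stands, and is a reason for the sponsor to choose and justify the contrast.

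Fourth, SPPB is bounded at 0 and 12. A score uniform over 0 to 12 has SD 3.74, and a normal distribution centred at 6 with SD 4.2 would put about 15% of values off the scale. The half-widths in points and the power figures are therefore approximate. The percentage variance cuts do not depend on the SD.

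Finally, ANOVA software also prints means and error variance. It does, but the plan commits to reporting none of them, and output does not choose a primary contrast.

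**Conclusion.** The concern holds. Baseline SPPB is one of three responses, and no single between-group effect with a CI is prespecified. Baseline adjustment would usually be more precise. Against change from baseline, the variance falls by 8% to 23% at T1 and by 11% to 31% for the T1/T2 average, for correlations of 0.8 down to 0.5. At 0.9 the gain at T1 is about 2%, and by 0.95 it is nil. These figures rest on an assumed correlation, compound symmetry, normality and complete data.

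This is a matter of precision and interpretability, not validity. The change should be made, but it does not invalidate the plan as written. Confidence is medium, because the size of the gain depends on a correlation that the documents do not give.

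**What to change.** - Model SPPB at T1 and T2 as responses, with group, time, group-by-time, baseline SPPB and baseline-by-time as terms. Report the between-group difference with its 95% CI.
- Before outcome data are seen, name and justify one primary contrast: the T1/T2 average, which fits the plural wording of the sample-size paragraph, or T1. Report the remaining time-point differences as secondary.
- Commit to reporting the residual SD and the baseline-to-follow-up correlation.
- Adjust each continuous secondary outcome for its own baseline.
- Describe baseline characteristics by group without significance tests.

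The cost is one residual degree of freedom (37 instead of 38) and no new data or visits. It is more than an edit of wording, because the sponsor must decide which effect the pilot is to estimate. The average gives up power if the effect is present at one time point only, and T1 alone gives it up if the effect grows after the intervention ends.

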Cardiac-specific functional status: The Seattle Angina Questionnaire will be used to measure cardiac-related functional status. It has 19 items in 5 subscales: physical limitation, angina stability, angina frequency, treatment satisfaction and disease perception.³² It is scored on a 1–5 or 6 sequentially coded scale and subscale scores are transformed to a scale of 0–100, with higher scores indicating higher levels of functioning and fewer limitations. The Chinese version has been shown to be reliable, valid, and sensitive to clinical change.³²

Cardiac-specific HRQoL: The MacNew will be used to measure cardiac-specific HRQoL.³³ It has 27 items scored on a 1-7 scale, and then global score is calculated by summing the item scores, with higher scores representing better HRQoL. MacNew has good internal consistency, test-retest reliability, concurrent and discriminant validity.³³

Psychological distress: The Patient Health Questionnaire-4 (PHQ-4)³⁴ will be used to measure psychological distress. It consists of 4 items assessing anxiety and depression, to be responded on a 4-point Likert scale. The composite total score ranges from 0 to 12, higher scores indicate greater level of anxiety and depression. It has good psychometric properties.³⁴

MACCE and hospital readmission rates: will be monitored from enrollment to the study to 3 months after the intervention through record review.

Data collection procedure and randomization

Ethical approval will be obtained from the institutional review board. Active recruitment strategies will be used by posting recruitment notes on the newsletters and Facebook of the

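### The p<0.05 rule covers every secondary outcome with no adjustment, order or exploratory status, so a null intervention has roughly a 13% to 37% chance of a significant secondary

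*Combined protocol and SAP*

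**What the plan says.** The combined protocol and SAP ranks the outcomes once, under Outcome evaluation: "Physical performance will be the primary outcome, while the rest will be the secondary outcomes". The end of the Background section gives the same ranking. Physical performance is measured by the SPPB, which is also the basis of the sample size under Study setting and participants.

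The continuous secondaries under Outcome evaluation are appendicular muscle mass, grip strength, the Seattle Angina Questionnaire, the MacNew global score and the PHQ-4 total. Of the angina questionnaire the plan says "It has 19 items in 5 subscales: physical limitation, angina stability, angina frequency, treatment satisfaction and disease perception", and that "subscale scores are transformed to a scale of 0–100"; it defines no total score. MACCE and hospital readmission are collected by record review.

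The Data analysis section names one method for outcome comparisons: "Repeated measure ANOVA will be used to determine the effects of the intervention by comparing differential between group changes across the 3 time-points". It then sets the threshold: "All statistical tests will be two-sided, and a p-value of less than 0.05 will be considered statistical significant". Nothing in the document adjusts for several secondary tests, orders them, or says that their p-values are descriptive.

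**The concern.** A 5% threshold limits the false-positive risk of one test. Applied separately to several secondary outcomes, it does not limit the chance that at least one of them crosses the line. The Data analysis section uses the ANOVA to determine intervention effects and makes no distinction between primary and secondary outcomes when it says what counts as significant.

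At stake is what the report may say. A non-significant SPPB beside one secondary with p<0.05 is a realistic outcome for a trial of this size. Under the current wording that secondary is a statistically significant effect of the intervention, and the plan has no rule for reading it more cautiously.

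**Working it through.** **1. Inputs from the document.** Alpha 0.05, two-sided, for every test (Data analysis). Twenty participants per arm (Study setting and participants). Three time points, with repeated-measures ANOVA comparing change between groups (Data analysis). I take this as one group-by-time test per outcome.

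**2. Number of tests.**
- By named outcome: muscle mass 1 + grip strength 1 + Seattle Angina Questionnaire 1 + MacNew 1 + PHQ-4 1 = 5.
- With each questionnaire subscale tested: 1 + 1 + 5 + 1 + 1 = 9.
- MACCE and readmission are left out. Repeated-measures ANOVA does not fit them and no other outcome test is named. If Fisher's exact test were used at 20 per arm, its actual size would be only 0.2% to 2.3% each for assumed event rates of 5% to 20%, so they would add little.

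**3. The plan's own figure.** The plan states 5% per test and gives no error rate for the set of secondaries. In simulation under no effect, the per-test rejection rate of the group-by-time F test is about 5%, so the stated level holds for each test taken singly.

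**4. Independent tests.** The chance of at least one p<0.05 among k tests is 1 − 0.95^k.
- k = 5: 1 − 0.774 = 22.6%
- k = 9: 1 − 0.630 = 37.0%

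**5. Correlated tests.** The secondaries will be correlated to some degree, which lowers the figure. The documents give no correlation, so a range is needed. Two calculations were made:
- *z tests:* for equally correlated two-sided z tests with correlation ρ and c = 1.96, the chance is 1 − ∫ φ(u) [Φ((c − √ρ·u)/√(1−ρ)) − Φ((−c − √ρ·u)/√(1−ρ))]^k du.
- *F tests:* simulation of the group-by-time F(2, 76) test, with 20 per arm, three visits, an assumed within-person correlation of 0.6 and 20,000 replicates per setting.

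| Assumed ρ between outcomes | 5 tests, z | 5 tests, F | 9 tests, z | 9 tests, F |
|---|---|---|---|---|
| 0 | 22.6% | 22.4% | 37.0% | 37.1% |
| 0.3 | 20.9% | 21.3% | 32.6% | 33.1% |
| 0.5 | 18.3% | 18.7% | 26.9% | 27.7% |
| 0.8 | 12.7% | 13.1% | 16.5% | 17.4% |

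Raising the within-person correlation to 0.8 leaves the nine-test figure at ρ = 0.5 at about 28%.

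**6. Size against the stated level.** The lowest case is 13% / 5% = 2.6 times the nominal level. The highest is 37% / 5% = 7.4 times.

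**7. How likely a null SPPB is.** The 80% power in the sample-size paragraph belongs to the future main trial. A simple two-group comparison with 20 per arm has about 14% power at the stated standardized effect of 0.28, and about 11% at 1/4.2 = 0.24. This is a rough guide, because the power of the planned ANOVA depends on correlations that are not given.

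**The case against.** The strongest reply is that this is a 40-person pilot. Its stated aim is feasibility and a preliminary look at effects, its sample size serves the later trial, and no sentence commits the team to claiming efficacy from a secondary outcome. With one primary outcome, the primary claim needs no error control across the secondaries. This stands, and it is why the point is minor. It does not remove the point, because the aim does not alter the operative rule in Data analysis.

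Several stronger readings are tempting, and the document does not support them:
- **That there is no hierarchy at all.** The SPPB is ranked above everything else in two places. What is missing is an order, adjustment or exploratory status among the secondaries.
- **That there are at least nine tests.** This requires each angina questionnaire subscale to be tested. The plan describes how the subscales are scored and does not say that each is tested; the Background lists cardiac-related functional status as one outcome.
- **That the false-positive chance is 28%.** That figure needs nine tests and a between-outcome correlation near 0.5. Neither is in the document.
- **That false secondaries will steer the redesign.** The closing sentence of Data analysis about optimising the intervention follows directly on the sentence about qualitative data and most naturally refers to those data.
- **That a formal adjustment across the secondaries is required.** It would need a test count that the plan has not set.

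One modelling objection also stands. Participants must be free of ischemic symptoms in daily activities, so some angina subscales may sit near their ceiling. The calculations assume well-behaved continuous scores and do not address this.

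**Conclusion.** The concern holds in a limited form. The threshold applies to all secondary tests, and the plan neither adjusts for them, orders them nor labels them exploratory. If the intervention has no effect, the chance of at least one significant secondary is about 13% to 23% with five tests and 17% to 37% with nine. The range rests on assumed equal correlations between outcomes from 0.8 to 0, one group-by-time test per outcome and approximately normal scores; the choice between five and nine rests on how the angina questionnaire is analysed. The primary SPPB comparison is unaffected. Severity is minor.

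**What to change.** In Data analysis, limit the p<0.05 significance statement to the SPPB comparison. Add that all other outcomes are exploratory, will be reported as between-group differences with 95% confidence intervals, and will not be described as statistically significant effects. This agrees with the trial's preliminary aim, and it works whether the angina questionnaire yields one comparison or five.

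The cost is one or two sentences, with no extra participants, data or procedures. The downside is that an isolated nominal p<0.05 on a secondary can no longer be reported as a significant effect.
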